Establishing the Effectiveness of Publicly Available Smoking Cessation Resource

Study Protocol and Data Analysis Plan

PI: [name], PhD

ClinicalTrials.gov ID: NCT05055778

Funding: This study was funded by the National Center for Advancing Translational Sciences of the National Institutes of Health under Award Number KL2TR003016. [name] was an iTHRIV Scholar during the completion of this work. The iTHRIV Scholars Program is supported in part by the National Center for Advancing Translational Sciences of the National Institutes of Health under Award Numbers UL1TR003015 and KL2TR003016.

List of Abbreviations

NCI: National Cancer Institute

SFTXT: Smokefree.gov Initiative SmokefreeTXT smoking cessation text message intervention

Study Overview

This project will recruit smokers from across Virginia with recruitment from rural and non-rural counties. All participants will be provided with access to a research version of the National Cancer Institute's SmokefreeTXT program (SFTXT). Cessation outcomes will be assessed at the end of program (7-weeks), and 3- and 6-months from enrollment. We will compare smoking abstinence by rurality. The project will be conducted remotely, using study-specific websites to complete all data collection, and using participants' own phones for intervention implementation.

Study Recruitment

Participants will be recruited using targeted (by location and likelihood of being a smoker) Google advertisements, social media (e.g. Facebook), and via introduction by a representative of a community partner organization. People interested in learning more about the study will be able to click through to a secure study-specific Qualtrics page which will serve as the study website. The website will include all information needed for informed consent and, for eligible participants, will serve as the consent form. It will provide an overview of the study and describe all aspects of study participation, risks, and benefits.

The information page will also serve as an eligibility screener. The screening component of the webpage will be divided into two parts. The first part will include items to assess eligibility and monitor demographic distribution of potentially interested participants. This includes assessing current smoking status, cell phone ownership, ability to read and speak English, current pregnancy status and planned pregnancies, date of birth, race, ethnicity, and gender identity. Individuals who do not meet initial study eligibility criteria will be informed that they do not qualify for the study. Interested participants who appear eligible at this stage will then be asked to provide additional contact information and will be asked to consent to participate in the study. The additional questions are, full name, home address, phone number, email address, and consent to be contacted via email. This information will be used for final eligibility determination. The age and identity of all individuals will also be confirmed using an online people search vendor. Individuals who do not meet study eligibility criteria due to non-Virginia residence or whose identities cannot be verified will be emailed to inform them they do not qualify for the study.

The inclusion criteria are:

- English speaking adult (18+ years old)
- Current cigarette smokers (at least 5 cigarettes per day)
- Residing in Virginia
- Owns a cell phone
- Is interested in quitting smoking but not currently undergoing a quit attempt

The exclusion criteria are:

- Being pregnant or anticipate becoming pregnant in the next 6 months

Rurality will be determined by utilizing Rural Urban Commuting Area codes. Rural counties have been identified by the Office of Rural Health policy, which takes into account areas

determined to be Metropolitan Areas based on the Office of Management and Budget as well as specific census-track levels areas based on RUCA codes 4-10.

If the participant is deemed 'not eligible' at any point they will be notified either via Qualtrics or via email and tagged as 'not eligible' and the reason why noted in our electronic database. All ineligible participants, regardless of reason for exclusion, will be given a list of alternative treatment resources (smokefree.gov online resources and information on [name]).

After the informed consent process is complete, participants will be sent an email link to collect additional baseline data (pre-assessment) and text message enrollment instructions.

Study Assessments

Pre-Assessment: This assessment questionnaire includes questions about tobacco use, readiness to quit smoking, motivation to quit smoking, confidence in quitting, mood, cessation techniques used in the past and planned for future quit attempts, as well as general information about themselves (age, gender, race, etc.), general health behaviors (e.g., alcohol use), cell phone and technology use questions (e.g., type of phone, carrier, frequency of voice calls, frequency of text messaging, perceived quality of signal quality, etc.), and measures of social cohesion and unmet needs. It is estimated that the Pre-Assessment Questionnaire will take 30 minutes. Participants will receive daily e-mail prompts to complete the Pre-Assessment Questionnaire until it is complete, or until three days have passed since their enrollment date.

After the Pre-Assessment Questionnaire is complete, the program automatically advances participants to text message enrollment instructions. Participants are instructed to text "JOIN" to the study text message platform via a study specific verified toll-free phone number. They will then complete the enrollment process through their own phones and begin receiving 3-5 messages a day for 7 weeks. Participants will be asked to sign up for the text messaging program within three days of completing the pre-assessment. All participants will receive reminder emails to complete text program enrollment for 3 days after the completion of the pre-assessment. Study staff will contact participants if they completed the baseline questionnaire but after three days have no record of completing the text program enrollment.

Post-baseline Assessments: At the end of the 7-week intervention, 3 months after the quit day, and 6 months after the quit day, participants will be instructed (by email) to

complete online follow-up assessments. The assessment questionnaires include questions about tobacco use, reasons for relapse (if relevant) motivation to quit smoking (if relevant), confidence in quitting (if relevant), mood, cessation techniques used in the previous assessment period, alcohol use, as well as satisfaction with the intervention and any changes in cell phone and technology use (e.g., type of phone, carrier, frequency of voice calls, frequency of text messaging, perceived quality of signal quality, etc.). The Post-Assessment Questionnaires are estimated to take no more than 20 minutes. As was true for the Pre-Assessment, participants will be able to complete the Post-Questionnaires in more than one sitting as the program auto saves where they are in the Questionnaire. Participants will be able to review and revise answers up until the point they select “Submit.” Once the Questionnaire data is submitted, participants will no longer have access to their responses on the Questionnaire. All participants will receive reminder emails to complete the assessments daily for 3 days after the invitation to participate is sent.

Intervention

SFTXT is a six- to eight-week program that takes place entirely on a user’s cellphone. Adults who interested in quitting smoking register for the program either online or by texting the program directly and select a quit day up to two weeks in the future. Between enrollment and the quit day, three to five messages are sent each day in preparation for the quit attempt. Starting on the quit day, users continue to receive multiple messages a day for six weeks. Within-program assessment questions texted to users measure smoking status, mood, and craving levels. Users are also able to request on-demand help using “keywords” related to smoking, mood, and cravings. Use of a keyword returns one of several preprogrammed responses. In practice, users are told about the keywords initially and are given reminders about some or all of the keywords within the program on Days 1,6, 10, 14, 17, 20, and 35. Users may opt out of the program at any time by texting “STOP” and can restart the program with a new quit date by texting “NEW”. SFTXT is one of the most popular publicly available text-messaging cessation interventions, with more than 150,000 smokers having enrolled since 2011.

For the purposes of this study, all messages from SFTXT have been reprogrammed into a study specific account on a third party text message vendor, TextIT, and administered through a verified phone number via Twilio. This will allow better control of text message delivery and data by study staff, while maintaining all program functionality. For study participants, the initial quit date is set at one week after enrollment, but participants may change their quit date at any time by texting “NEW”.

Study End

After completion of the 6-month survey, participants will be told that they have reached the end of the study. Participants who do not respond to the invitation to complete the 6-month post-assessment after four reminder emails will be sent an email informing them that they have reached the end of the study

Participant incentives

Participants will receive up to \$100 for participating in the study in the form of e-gift cards sent at three time points:

- Up to \$30 at the end of the intervention
 - \$10 for completing the pre-cessation survey
 - \$20 for completing the end of intervention survey
- \$30 for completing the 3-month survey
- \$40 for completing the 6-month survey

Data Analysis

This study was approved by the Social and Behavioral Sciences IRB at the University of Virginia (SBS IRB# 3928, clinicaltrials.gov identifier: NCT05055778).

Analysis of this study will be primarily descriptive in nature as there is only one intervention arm and no randomization

Outcomes of Interest

The post-intervention, three-, and six-month assessments measure the primary outcome of interest: 7-day smoking abstinence (responses to the question: “Have you smoked a cigarette (even a puff) in the past 7 days?”, with responses of ‘yes’, and ‘no’) measured at 7-weeks, 3-months, and 6-months. Secondary outcomes include continuous smoking abstinence (responses to the question: “In the last [6-weeks/3 months/6 months], have you smoked at all?”, with responses of ‘yes’, ‘no’, and ‘don’t know’). To provide the most conservative estimates of abstinence, missing responses for each assessment will be coded as continuing to smoke.

Statistical Analyses

Descriptive statistics will be used to characterize the population and describe primary and secondary cessation outcomes in the entire study population. All analyses will be conducted using SAS 9.4 (SAS Institute Inc., Cary, NC).

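### Coding every missing survey as smoking is not conservative for the promised rural comparison, and the plan has no response rates by rurality and no second missing-data analysis

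*Combined protocol and SAP*

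**What the plan says.** The Study Overview states one group comparison: "We will compare smoking abstinence by rurality".

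Under Outcomes of Interest, the primary outcome comes from three online surveys: "The post-intervention, three-, and six-month assessments measure the primary outcome of interest: 7-day smoking abstinence". Under Post-baseline Assessments, the invitation goes out by email, and so do the reminders: "All participants will receive reminder emails to complete the assessments daily for 3 days after the invitation to participate is sent". For the 6-month survey, Study End gives a different count: "Participants who do not respond to the invitation to complete the 6-month post-assessment after four reminder emails will be sent an email". Payments of $20, $30 and $40 are attached to the three follow-up surveys. No closing date for a survey is given.

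The missing-data rule, also under Outcomes of Interest, is explicit: "To provide the most conservative estimates of abstinence, missing responses for each assessment will be coded as continuing to smoke". The Statistical Analyses paragraph then says: "Descriptive statistics will be used to characterize the population and describe primary and secondary cessation outcomes in the entire study population". It gives no method for the rural comparison, no response rates by wave or rurality, and no analysis under any other assumption about missing answers.

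**The concern.** The reason given for the missing-data rule is that it is conservative. That is correct for the abstinence rate of one group, because the rule can only pull the rate down. It does not carry over to a difference between two groups. Each group's rate is pulled down by an amount that depends on how many people did not answer and how many of those had in fact stopped smoking. If these amounts differ by rurality, the reported gap is wrong, and it can be wrong in either direction.

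Rural versus non-rural abstinence is the only contrast the documents state. With one missing-data rule and no response rates by group, a reader could not tell a gap in abstinence from a gap in survey response.

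**Working it through.** The documents give no sample size, response rate or abstinence rate, so the plan has no figure to reproduce. All rates below are assumed. Responders' answers are taken at face value, and the true rate means the rate that would be seen if everyone had answered.

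For each group, let r be the share who answer, a the abstinence among responders, and b the abstinence among non-responders.

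- Reported rate under the plan's rule: r × a.
- True rate: r × a + (1 − r) × b.
- Reported minus true, one group: −(1 − r) × b. This is never above zero, so the rule gives a lower bound for a single rate.
- Reported minus true, for the gap (non-rural minus rural): (1 − r_rural) × b_rural − (1 − r_nonrural) × b_nonrural. This can be positive, negative or zero. It is zero if b = 0 in both groups, or if the two terms cancel.

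**Unequal response, same b in both groups.** Take r = 0.70 rural and 0.80 non-rural, with a = 0.20 in both. Reported: 0.70 × 0.20 = 14% and 0.80 × 0.20 = 16%, a gap of 2 points. Responders-only: 20% v 20%, a gap of 0.

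| b | True rural | True non-rural | True gap | Error in reported gap |
|---|---|---|---|---|
| 0% | 14 + 0 = 14% | 16 + 0 = 16% | 2 | 0 − 0 = 0 |
| 10% | 14 + 3 = 17% | 16 + 2 = 18% | 1 | 3 − 2 = 1 |
| 20% | 14 + 6 = 20% | 16 + 4 = 20% | 0 | 6 − 4 = 2 |

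The plan's rule reports 2 points and the responders-only analysis reports 0 in every row. The observed data alone cannot say which row is right.

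**Same case, b allowed to differ by group.** With b = 20% rural and 0% non-rural, the true rates are 20% v 16%, a gap of −4. With b = 0% rural and 20% non-rural, they are 14% v 20%, a gap of +6. Over the range from 0% to the responders' rate, a reported gap of 2 points is therefore compatible with anything from −4 to +6.

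**Equal response is not enough.** With r = 0.80 in both groups, b = 10% rural and 0% non-rural, the error is 0.20 × 10 − 0.20 × 0 = 2 points.

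**The rule can also hide a gap.** Suppose true abstinence is 25% non-rural and 20% rural, non-responders resemble responders in each group, and response is 56% and 70%. The reported rates are 0.56 × 25 = 14% and 0.70 × 20 = 14%. A true 5-point gap is reported as none.

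**A wider response gap.** With response 50% rural and 70% non-rural, and a = 25% in both, the reported rates are 12.5% and 17.5%, a gap of 5 points. With b = 0%, 10% or 25% in both groups, the true gap is 5 points (17.5 − 12.5), 3 points (20.5 − 17.5) or 0 points (25 − 25).

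**The case against.** The rule is openly declared, and it gives a valid lower bound for the whole-population rate, which is what the Statistical Analyses paragraph sets out to describe. If no non-responder is abstinent, which is what the rule assumes, the rural gap carries no error at all. The study calls itself mainly descriptive, with one arm and no randomization, so no formal test depends on this. The rural comparison is one sentence in the overview with no method behind it, and that omission comes before any question of sensitivity analysis. The survey payments should help retention.

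Most of this stands. It is why missing-as-smoking can stay as the main analysis, and why the fix starts by writing the rural comparison down. It does not remove the point: descriptive rural and non-rural rates are distorted by the same arithmetic, and payments do not show whether response was equal.

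A reader might also infer that three days of reminders loses outcome data and that the emails should be spread over a fixed window. The documents do not support that. Three days is a reminder period, not a closing date, and nothing shows that later answers are refused or that spaced emails would bring in more of them. A fixed window could turn usable late answers into counted smokers. It would also shift recall. With the default quit day one week after enrollment (day 7), a six-week question answered at day 49 reaches back to 49 − 42 = day 7. If a 14-day window let it be answered at day 63, it would reach back only to 63 − 42 = day 21.

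**Conclusion.** The point holds as a gap in the analysis plan. The stated justification covers a single rate and does not cover the one comparison the overview promises. That the safeguards are absent is clear from the text. How much this matters is not known: with the assumed rates above, the error in the rural gap runs from 0 to 2 points when non-responders are alike in the two groups, and from −4 to +6 points for the true gap when they are not. The upper limit rests on the further assumption that non-responders are no more often abstinent than responders.

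Two stronger conclusions should not be drawn. The documents do not show that rural participants respond less, so unequal response is a possibility and its direction is open. Nor is missing-as-smoking a wrong choice; it is insufficient on its own for a contrast. The change should be made because it is cheap and decides what the rural comparison can support.

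**What to change.** In Statistical Analyses:

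1. Add the rural v non-rural description of abstinence at 7 weeks, 3 months and 6 months.
2. Keep missing-as-smoking as the main analysis.
3. Report the response rate at each wave by rurality.
4. For each group, show the responders-only result, and a grid of assumed abstinence among non-responders from 0% to that group's responders' rate, varied separately by group. The main analysis and the responders-only result are two corners of this grid.
5. Limit the word conservative to the single-group rates.

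The cost is a few extra tables from data already collected. The funding statement's past tense suggests that follow-up may be finished; the additions are still possible then, and should be labelled as added afterwards if outcomes by rurality have been seen. No change to the timing of reminder emails is needed.

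Two separate minor inconsistencies should be reconciled: the reminder count (three days of daily emails under Post-baseline Assessments, four emails under Study End), and the time anchor for the 3- and 6-month surveys (enrollment in the Study Overview, quit day under Post-baseline Assessments).

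### The fixed look-back in the continuous-abstinence item can take in smoking from before a postponed quit day, and the plan does not say whether surveys follow the new date

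*Combined protocol and SAP*

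**What the plan says.** Under Outcomes of Interest, continuous smoking abstinence is a single self-report item: "In the last [6-weeks/3 months/6 months], have you smoked at all". It does not mention the quit day. The same paragraph places the outcome assessments at 7 weeks, 3 months and 6 months.

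The Intervention section says that, for study participants, "the initial quit date is set at one week after enrollment", and that "participants may change their quit date at any time by texting" NEW. The general description of the program says users "can restart the program with a new quit date by texting" the same keyword. For the study version, no limit is given on how often or how far the date may move.

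Survey timing is stated in two ways. Study Assessments has surveys "At the end of the 7-week intervention, 3 months after the quit day, and 6 months after the quit day". Study Overview times the 3- and 6-month assessments from enrollment instead. Neither place says what happens to survey dates when the quit day moves.

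On the day of answering, Study Assessments says: "All participants will receive reminder emails to complete the assessments daily for 3 days after the invitation to participate is sent". Study End refers to four reminders for the 6-month survey and then an end-of-study email. No closing date for a response is stated for any survey.

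**The concern.** A reader of the results will take continuous abstinence to mean no smoking since the quit attempt began. The item measures something else: no smoking over a fixed span ending on the day of answering. The two agree only when that span happens to begin on the quit day.

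If the quit day is postponed and the survey is not re-timed, the span reaches back into days when the participant was still expected to be smoking. A fully successful quitter is then recorded as not continuously abstinent, and the item alone cannot separate that answer from a true relapse. If the survey is answered late, the first days after quitting fall outside the span and an early lapse can be missed. The errors run in opposite directions and depend on what participants do, so they cannot be assumed to cancel. This item is the only stated measure of a named secondary outcome.

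**Working it through.** The plan gives no sample size, power or event figure for this point, so the check is date arithmetic.

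**Inputs**
- Day 0 is text-program enrollment, taken here as the enrollment that Study Overview means (assumption).
- Initial quit day: day 7 (Intervention).
- Look-back L: 42 days at week 7, then 3 and 6 months (Outcomes of Interest).
- Week-7 survey: day 49 if it stays on the calendar.
- k: days by which the quit day is moved later. The documents give no values; 7, 14 and 28 are assumed as a range.
- d: days from invitation to answer. Three daily reminders give d = 3, and four at 6 months give d = 4. A value of 14 is assumed to show a long delay.

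**Formula**

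Offset = (survey day + d − L) − (7 + k)

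A negative offset means that pre-quit days are inside the look-back. A positive offset means that the first days after quitting are outside it.

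**Default case at week 7** (k = 0, d = 0): 49 − 42 = day 7, and 7 − 7 = 0. The match is exact.

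**Postponed quit day, answered on the day of invitation** (d = 0), offsets in days:

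| Survey timing | Formula | k = 0 | k = 7 | k = 14 | k = 28 |
|---|---|---|---|---|---|
| Week 7 fixed at day 49 | d − k | 0 | −7 | −14 | −28 |
| 3 and 6 months from the initial quit day | d − k | 0 | −7 | −14 | −28 |
| 3 and 6 months from enrollment | d − 7 − k | −7 | −14 | −21 | −35 |
| All surveys follow the current quit day | d | 0 | 0 | 0 | 0 |

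For k = 7 at week 7, the quit day is day 14 and the look-back starts on day 7. Pre-quit days number 14 − 7 = 7, and 7/42 = 16.7% of the look-back. Entry requires at least 5 cigarettes a day, so smoking in that week is the expected case and the truthful answer is yes.

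The third row matters even without postponement. If the 3- and 6-month surveys run from enrollment, a participant on the default schedule who answers promptly has 7 pre-quit days in both look-backs.

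If surveys follow the new quit day, the program ends on day 14 + 42 = 56, and 56 − 42 = day 14. The postponement error is gone.

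**Late answer, quit day not moved, survey timed to it**: offset = +d. At week 7 with d = 3, (49 + 3) − 42 = day 10, so 3 days are lost. At 6 months with d = 4, 4 days are lost. With the assumed d = 14, 14 days are lost. The error changes a classification only for someone who lapsed solely in those first days.

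**NEW after a relapse**: suppose a participant quits on day 7, smokes on day 10, and then sets a new quit day of 28 (assumed days). If surveys follow the latest date, the end-of-program survey falls on day 28 + 42 = 70 and its look-back starts on day 28. The day-10 relapse is not seen. Re-timing alone therefore does not settle what is measured.

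**Share affected**: if a proportion p postpones and surveys are not re-timed, the recorded week-7 rate cannot exceed 1 − p when answers are prompt. For illustration only, p = 5% gives a ceiling of 95% and p = 15% a ceiling of 85%. The documents give no value for p.

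**The case against.** The strongest reply is that the plan never defines the outcome as abstinence since the quit day. It defines it as the answer to a fixed look-back question, which is a legitimate choice. That stands: this is a gap between label and measurement, not a contradiction of a stated definition.

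Second, the larger error depends on survey timing. Study Assessments can be read as tying surveys to the quit day, and NEW as restarting the program, in which case postponement does no harm. That reading is available, but the text does not settle it. Outcomes of Interest states the first assessment as 7 weeks, and Study Overview times the later ones from enrollment.

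Third, late answering is a small matter within the stated reminders. That also stands.

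A reader might infer more than the documents support:
- *That the item fails even when every survey is timed to the participant's current quit day.* Only the late-answer shift, and the treatment of NEW after a relapse, remain in that case.
- *That analysts could not repair the outcome afterwards.* The full questionnaire is not given, in-program texts ask about smoking status, and study staff hold the text-platform data, so this is not shown.
- *That the rural comparison is biased.* Signal quality or technology use could affect rescheduling or prompt response, but nothing in the documents shows a difference.

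**Conclusion.** The point holds as a measurement gap in one secondary outcome. The fixed look-back equals abstinence since quitting only for an unmoved quit day and a same-day answer, with surveys timed to that quit day. A 7-day postponement with the week-7 survey left in place puts 7 of 42 days before the quit day and forces a yes from someone abstinent ever since. This assumes that the survey is not re-timed, that the participant smoked in the pre-quit week, and that the answer is prompt. Late answering is a minor effect of 3 to 4 days within the reminders, although no outer limit is stated.

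The number of participants affected is unknown. The primary 7-day outcome does not depend on the quit day and is unaffected. The study is single-arm and mainly descriptive, so no test or error rate is at risk. What is at stake is the meaning and accuracy of a reported abstinence rate.

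**What to change.** 1. Reconcile Study Overview and Study Assessments on whether the 3- and 6-month surveys run from enrollment or from the quit day, and state whether any survey date moves when the quit day does.
2. Keep the fixed look-back item and add one with a date filled in by the survey platform: *Since your quit day, [date], have you smoked any cigarette, even a puff?*
3. Define that date from time stamps alone. Use the last quit date set before a scheduled quit day first passes. A later NEW does not reset it, so a relapse after the first quit day still counts. The rule does not need the reason for texting NEW, which the documents do not describe as being recorded.
4. Score anyone whose quit date has not arrived by the survey as not abstinent.
5. Store the submission date, and report the time from quit date to answer. If surveys stay on the calendar, abstinence durations will differ between participants: 49 − 14 = 35 days for a 7-day postponement, against 42 by default.
6. Report both measures, labelling the fixed item as abstinence over its stated look-back. This preserves comparison with studies that use a fixed period.

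The cost is one extra survey item, a date link from the text platform to the survey, and a short IRB modification. The intervention itself does not change.

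### The 3- and 6-month surveys are timed from enrollment in one place and from the quit day in another; on the enrollment timing, the continuous-abstinence question also covers the week before quitting

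*Combined protocol and SAP*

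**What the plan says.** **Survey timing.** The Study Overview has cessation assessed at the end of the program (7 weeks) and at "3- and 6-months from enrollment". The Post-baseline Assessments paragraph of Study Assessments has participants invited at the end of the 7-week intervention and then "3 months after the quit day, and 6 months after the quit day". Outcomes of Interest names the waves only as 7 weeks, 3 months and 6 months, which does not settle the starting point.

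**Quit day.** The last paragraph of Intervention says that "the initial quit date is set at one week after enrollment" and that participants may change it at any time by texting NEW. It does not say whether survey dates then move.

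**Outcome.** Continuous abstinence is taken from the answer to "In the last [6-weeks/3 months/6 months], have you smoked at all". The look-back is a fixed length at each wave. Nothing tells participants to count from their quit day, and there is no grace period.

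**Smoking before the quit day.** The inclusion criteria require "Current cigarette smokers (at least 5 cigarettes per day") and "Is interested in quitting smoking but not currently undergoing a quit attempt". The Intervention section adds: "Between enrollment and the quit day, three to five messages are sent each day in preparation for the quit attempt".

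**The concern.** The two timing statements cannot both hold when the quit day falls a week after enrollment, and the difference affects more than the calendar. The look-back at 3 and 6 months is as long as the nominal survey interval, so it reaches back to whatever event the survey is timed from. If that event is enrollment, the question covers a week in which the plan itself expects participants to smoke.

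A participant who does what the program asks, stopping on the assigned day and not smoking again, would then truthfully answer *yes* and be counted as a failure on continuous abstinence. This would happen at 3 and 6 months but not at 7 weeks, so part of any fall in continuous abstinence between 7 weeks and 3 months could be an artifact of timing.

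**Working it through.** **Inputs.** Day 0 is enrollment. The default quit day is day 7 (Intervention). Look-backs are 6 weeks (42 days), 3 months and 6 months (Outcomes of Interest). I take 3 and 6 months as 91 and 183 days; this choice does not affect the overlap, because survey interval and look-back are equal and cancel.

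**Check of the plan's own timeline.** One week before the quit day plus the six weeks in "Starting on the quit day, users continue to receive multiple messages a day for six weeks" gives 1 + 6 = 7 weeks, which agrees with the stated 7-week program.

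**Formula.** Pre-quit days in the window = max(0, quit day − (survey day − look-back)).

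| Wave | Enrollment schedule | Quit-day schedule, date unmoved |
|---|---|---|
| 7 weeks | 7 − (49 − 42) = 0 | 7 − (49 − 42) = 0 |
| 3 months | 7 − (91 − 91) = 7 | 7 − (98 − 91) = 0 |
| 6 months | 7 − (183 − 183) = 7 | 7 − (190 − 183) = 0 |

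On the enrollment schedule the windows of 91 and 183 days therefore hold 91 − 7 = 84 and 183 − 7 = 176 post-quit days. The pre-quit share is small (7/91 = 7.7% and 7/183 = 3.8%), but it does not measure the bias, because a single cigarette in the window changes the answer. At the entry minimum, and assuming smoking continues unchanged, the pre-quit week holds at least 7 × 5 = 35 cigarettes.

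**Sensitivity of the 7 days.**

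- *Late answers.* On the enrollment schedule, an answer given L days late leaves max(0, 7 − L) pre-quit days: 4 at three days late, 3 at four days, none from seven days on.
- *Meaning of enrollment.* If the surveys count from study entry but the quit date counts from joining the text program, the overlap grows by the gap between the two. Using the three days of prompts for the pre-assessment and the three days for joining as an illustration, it is 3 + 3 + 7 = 13 days. These are reminder and request periods, not limits, so the documents set no upper bound.
- *Quit date moved by NEW.* Suppose the date moves later by d days and the surveys stay put. The 7-week window then holds d pre-quit days. The 3- and 6-month windows hold 7 + d on the enrollment schedule and d on a schedule tied to the initial quit day. For d = 7 or 14 (assumed), this is 7 or 14 at 7 weeks, and 14 or 21 at 3 and 6 months on the enrollment schedule.

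**Primary outcome.** The 7-day question does not reach back to the quit day. The conflict changes only the time since the default quit day: 84 versus 91 days at 3 months, and 176 versus 183 days at 6 months.

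**The case against.** The strongest reply is that the bias arises only under the less likely of the two statements. The Post-baseline Assessments paragraph is the operational text, and the exact fit of the 6-week question to the 7-week survey suggests that the look-backs were built around the quit day. On that view the Study Overview contains one loose sentence and no result is harmed. This stands as a reason to correct the Study Overview rather than the assessment section. It does not remove the conflict, since anyone following the Study Overview would obtain a different measure.

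A second reply is that the plan defines the outcome only as the answer to a fixed question, so *yes* is the correct answer to what was asked. That is literally true. The item would still fail to measure abstinence after quitting, and it would mean different things at different waves. The plan's stated wish for conservative estimates concerns missing responses and does not cover people who answer truthfully.

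Third, late answers, early quitting and loose recall of dates all shrink the effect. They do, and its extent is therefore unknown.

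Finally, this is a secondary outcome in a single-arm study that calls its analysis mainly descriptive, and the funding statement's past tense suggests that the work may be finished. These points limit the consequences and bear on which remedy is available; they do not make the timing consistent.

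**Conclusion.** The concern holds. The plan gives two incompatible starting points for the 3- and 6-month surveys. On one of them, the continuous-abstinence question includes 7 pre-quit days at both waves, against none at 7 weeks. On the other, with an unmoved quit date, there is no overlap at any wave. Any bias is downward, and the number of participants affected cannot be derived from the documents.

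The 7 days assume that enrollment means the same event throughout, that the quit date stays at its default and that the survey is answered on time. Misclassification further assumes that the participant smokes during the pre-quit week and reads the question literally. The contradiction is certain; whether any bias occurred depends on which schedule was run. The plan should be corrected on this point, although the primary outcome item is not distorted.

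**What to change.** Establish first which schedule is in use or was used.

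**If the surveys can still be timed.** Correct the Study Overview sentence so that the 3- and 6-month surveys count from the quit day, as in Post-baseline Assessments, and keep the fixed look-backs. Add one sentence stating whether the quit day is the initial date or the latest date after NEW, and use the same date for survey timing and for continuous abstinence.

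**If the surveys have already gone out on the enrollment schedule.** State that starting point, and report that continuous abstinence at 3 and 6 months includes the pre-quit week and is therefore understated.

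**Cost.** One corrected sentence and one added sentence, with no new question and no new data. Relative to the Study Overview, the surveys fall a week later, on days 98 and 190 instead of 91 and 183. Using the initial date counts people who delay quitting as not continuously abstinent; using the latest date makes survey dates and study length vary between participants. For surveys already completed, *yes* answers caused by pre-quit smoking cannot be recoded, only disclosed.
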